responses are seen in the initial RET+ cohort but FGFR1+ responses or FGFR PD modulation have been noted at 45mg and 45mg appears acutely well tolerated per DLT criteria we will reconsider this logic and accrue an additional RET+ cohort at 45mg. If doses other than 45mg QD are explored, the number of patients in each biomarker selected cohort will be modified to include only those treated at the final ‘biologically selected dose’ (i.e. the tolerable dose associated with evidence of FGFR pathway pharmacodynamic modulation or of radiographic responses in FGFR biomarker selected cohorts) and the response rates in each biomarker selected cohort will be calculated within each cohort using only the number treated at this dose.

Objectives:

Primary:

Part A – To determine the prevalence of defined biomarkers in the screened patient populations.

Part B – To determine the objective response rate (ORR) (RECIST v1.1) to ponatinib at a ‘biologically selected dose’ in different molecularly defined cohorts of lung cancer.

Secondary:

Part A –

- 1) To determine the effectiveness of prescreening locally and nationally.
- 2) To determine the clinical and pathological features associated with biomarker positivity and negativity.

Part B –

- 1) To evaluate the safety, tolerability, and adverse event profile of ponatinib in patients with advanced lung cancer.
- 2) To determine the progression free survival (PFS), pattern of failure (CNS vs. extra-CNS) and response duration (in patients who achieve an objective response) of ponatinib in molecularly defined cohorts of patients with advanced lung cancer treated at the ‘biologically selected dose’.
- 3) To compare the ORR in biomarker positive cohorts to the FGFR1 double negative cohort.

Tertiary/Exploratory:

- 1) To explore additional molecular mechanisms of initial sensitivity and resistance to ponatinib in patients with advanced lung cancer, including but not limited to addressing the impact of higher cutpoints/alternate patterns of FGFR1 copy number by SISH and mRNA levels by ISH on maximal percentage shrinkage per RECIST or PFS or duration of response in the FGFR1 copy number and/or mRNA positive cohorts; and the impact of FGF2 and/or 9 ligand mRNA levels by ISH on maximal percentage shrinkage per RECIST or PFS or duration of response in FGFR1 copy number and/or mRNA positive cohorts.

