A trial specific website and email and phone based contact information to a trial specific CRA will be established (Figure 10). The trial specific website will be hosted through the University of Colorado.

[figure not shown]
Figure 10

The website will prompt patients with advanced lung cancer, or those acting on their behalf, to fill out a series of questions (Initial Contact Decision Tree in Figure 11). If all answers are acceptable, contact details of both the patient (and a nominated second contact person) will be requested and a member of the study team will phone the patient and re-confirm the answers to determine suitability for remote consenting for molecular prescreening. The consenting process will include the use of the tumor sample for markers currently being tested in relation to ponatinib, future markers that may be developed in relation to ponatinib and future markers relating to other aspects of lung cancer biology. In addition it will cover retrospective and prospective access to clinical and demographic information including survival data and outcomes from other therapies. The website and other media sources will also offer direct phone contact to the study team.

Following consent for prescreening, either locally or remotely, the study CRA will acquire case notes to confirm ability (physically and financially) to travel to University of Colorado for clinical trial treatment, metastatic status and tumor type appropriate for the study. In eligible cases, the CRA will acquire the tumor block and/or unstained slides, plus any pre-existing stained slides, pathology reports or molecular test results on the same sample and pass to the Biobanking facility at CU. A pathologist will confirm the diagnosis and the specific histology and that there is sufficient material for molecular testing and distribute material to the CLIA-certified testing labs described for each marker in Appendix A. If insufficient tissue exists, we will send a letter to the patient and their MD explaining the pros and cons of rebiopsying with the decision deferred to the patient and their MD. The costs of rebiopsying will not be covered within the trial.

Figure 11: Initial Contact Decision Tree

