Perhaps the biggest potential pitfall associated with this study is the proposed use of Colorado as the only treatment site in the clinical trial. Traditional thinking dictates that when looking to enroll rare molecular subtypes into a clinical trial, multiple different study sites each recruiting a small number of patients should be involved. However, while this may be feasible for industry sponsored efforts, the cost and effort of starting up, maintaining and monitoring multiple sites when the primary site is holding the IND may not be feasible for most investigator initiated trials. Therefore, if high quality academically driven trials are to have a future, we have to change this model. In ‘Have Mutation, Will Travel,’ recognizing that many patients will now seek out the best treatment for their cancer over long distances, we proposed rethinking this traditional approach in favor of developing key ‘trials hubs’ designed to concentrate patients into a small number of centers. Beyond the logistical advantages of this approach, we also believe that clinical insights into the particular behavior of defined molecular subgroups and/or of a novel drug in such patients may more reliably come to light when clinical experience is concentrated across a small number of treating MDs. To illustrate this, we recently described the high incidence of rapid onset hypogonadism from crizotinib use in male patients with NSCLC, a previously unreported side-effect that came to our attention through consistent subtle clinical changes observed in the large group of ALK positive patients who had travelled to the University of Colorado for the early crizotinib trials (Weickhardt et al 2012). If web and other media-based information dissemination and remote consenting for molecular prescreening can really create a feasible new paradigm for conducting molecularly selected clinical trials, the most definitive way to prove it will therefore be to set the hurdle high and only employ a single clinical treatment site. However, if feedback from patients suggests that distance from Colorado is a major barrier to accrual, we will aim to open two other additional sites, one on the East coast and one on the West, choosing sites from pre-existing collaborations developed within the Lung Cancer Mutation Consortium. While the responsibility for multiple sites is outside the resources of this study, a total of three sites with optimal geographic spread would be feasible. If necessary we would also seek additional support from the Colorado SPORE, NIH, ARIAD pharmaceuticals and/or philanthropic foundations to facilitate the startup and maintenance of these extra sites.

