- Based on literature data: FGFR1 SISH will be positive in 6% SCLC (no information available on ISH probability).
- RET will be positive in 2% adenocarcinomas. However, in a pan-negative adenocarcinoma/NOS population this is estimated at 20% based on internal data at CU and these patients will be prioritized internally for RET FISH testing after FGFR1 testing over those who have other markers positive.
- Based on literature data: ALK will be positive in 4% adenocarcinoma (excluded from testing in trial).
- Based on literature data (Western population): EGFR mutations will be positive in 10% adenocarcinoma (excluded from testing in trial)

We assume, for practical purposes, EGFR, ALK, RET and FGFR1 marker positivity will behave as if mutually exclusive.

We assume 85% of marker positive patients will enter treatment cohorts.

We assume 5% of patients will be non-evaluable on treatment.

To populate each cohort with 12 evaluable patients, therefore 15 positive patients need to be identified and 13 treated.

22 (20 evaluable) patient FGFR1 double negative cohort (up to additional 36 across all cohorts, but likely mostly within FGFR1 double negative cohort if altered dosing required)

13 patient FGFR1 SISH+ve and ISH+ve cohort

13 patient FGFR1 SISH+ve and ISH-ve cohort

13 patient FGFR1 SISH-ve and ISH+ve cohort

13 patient RET+ve cohort

This makes a total of 74 patients (inc non-evaluable) on the initial treatment study, with up to 100 if additional cohorts are added.

To populate these cohorts will require 700 patients to be screened for FGFR1 SISH and ISH and 266 by RET FISH.

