10.2 Part A Analysis Plan

The goal of Part A is to determine the prevalence of each biomarker and the overlapping frequency of biomarkers (primary objective), which will guide on-going screening for selecting biomarker positive patients for the clinical trial to be conducted in part B. The association between biomarker positivity and the patient clinical and pathological features will be studied (secondary objective) to guide the selection process. In addition, the effectiveness of prescreening locally and nationally will be estimated (secondary objective). Interim analyses will be conducted after 250 and 500 screened samples, before the final analysis, to inform ongoing screening strategies. We will compare and contrast these with the data available from planned and ongoing analyses of tissue microarrays. With 700 samples, the maximum width (distance from the lower limit to the higher limit) of 95% confidence interval for the prevalence of a biomarker will be 0.075.

Biomarker prevalence and its 95% (exact) confidence interval (CI) among the screening patients and for different histologies will be reported. Overlapping frequency and its 95% CI between biomarkers among the screening patients and for different histologies will also be reported. The association between biomarker positivity and clinical/pathological features will be assessed using chi-square test, or Fisher's exact test if necessary, with the features including histology, age at diagnosis of current lung cancer (using age groupings as a categorical variable where necessary), age at diagnosis of metastatic lung cancer, race, sex, current stage, sites of metastatic disease at diagnosis, smoking status, EGFR, KRAS and ALK status. Biomarker prevalence will be reported for each category of features significantly

associated with biomarker prevalence. We will determine the impact of biomarker results on prognosis generating Kaplan-Maier survival curves for overall survival using log-rank testing to compare the survival distributions between marker positive and negative patients for each biomarker. In addition, we will determine the impact of the biomarker results on sensitivity or resistance to standard chemotherapies and patterns of metastatic spread as we have done before (Camidge et al, 2011; Doebele et al, 2012).

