APPENDIX A: BIOMARKER PRESCREENING

A1. Sample capture flowsheet

*Internal cases to d/w PI re RET FISH as pan-negatives to be prioritized

FGFR1 SISH, ISH and RET FISH are described. See Lab Manual for detailed Standard Operating Procedures. Comparable information derived from other assays, e.g. NGS platforms for RET rearrangements, may be permissible as an entry criterion, following discussion with the PI. In such cases, attempts to confirm with the study specific assays should be made.

Material sufficient for some but not all assays will still be considered acceptable and assays will be prioritized in the following order: *FGFR1* SISH, *FGFR1* ISH, *RET* FISH.

For equivocal or inconclusive cases, confirmatory assays (e.g. RT-PCR for RET rearrangements) may be conducted and if a conclusive result is generated, may be permissible as an entry criterion, following discussion with the PI.

Excess unstained slides of the requested 20 x 4uM and/or tumor block will be archived and consenting will permit additional biomarker analyses to be conducted pertaining to the biology of lung cancer and/or outcomes from this study.

A2. FGFR1 Copy number and message levels ([name] lab):

I. Protocol for SISH Assay

FGFR1 gene copy number is to be detected using Silver in Situ Hybridization (SISH) on the Benchmark® XT automated stainer (Ventana Medical Systems, Inc.). One unstained slide of the adequate ID is to be stained for FGFR1 SISH, and another unstained slide is to be reserved as backup in case of assay failure.

FGFR1/ CH8 SISH Procedure

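### Part A prevalence, the Part A primary objective, can be inflated because patients whose FGFR1 or RET status is already known are neither excluded nor reported separately

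*Combined protocol and SAP*

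**What the plan says.** The Part A primary objective (Section 1) is "To determine the prevalence of defined biomarkers in the screened patient populations". Section 10.2 defines the analysis set only in general terms: "Biomarker prevalence and its 95% (exact) confidence interval (CI) among the screening patients and for different histologies will be reported". It names no exclusion for prior test results.

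Four other places determine who can enter that set.

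- Section 5.2.1 excludes a known EGFR mutation or ALK rearrangement in adenocarcinoma. It does not mention a known FGFR1 or RET result.
- Appendix A1 says: "Comparable information derived from other assays, e.g. NGS platforms for RET rearrangements, may be permissible as an entry criterion, following discussion with the PI". It adds that confirmation on the study assay should be attempted, so an outside positive can become a study-assay positive.
- The Part B registration process in Section 13 asks for the Part A prescreen results, so a known positive who wants treatment is routed through Part A.
- Sections 5.1, 5.2 and 5.4 describe web outreach, remote consent and travel to one site, the last "recognizing that many patients will now seek out the best treatment for their cancer over long distances".

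Section 5.2 has the coordinator collect "any pre-existing stained slides, pathology reports or molecular test results on the same sample", but Section 10.2 gives prior FGFR1 or RET results no role in the prevalence estimate.

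**The concern.** A prevalence estimate assumes that the chance of entering the denominator does not depend on the marker. With open, patient-initiated recruitment to a marker-selected drug trial, a patient already told of a RET rearrangement or FGFR1 amplification has a strong reason to make contact. A patient already told of a negative result has much less. Nothing in Section 10.2 separates either of them from untested patients, and the exact interval covers sampling error only.

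Part A results are meant to steer continued screening, with looks after 250 and 500 samples, and are to be compared with tissue microarray data. Section 5.5 would consider dropping an FGFR1 screening subgroup after 100 or more patients without a positive; one self-referred known positive would prevent that. Known positives who come for treatment could also raise the share of positives who enroll, for which Section 10.2 sets a success mark of 85%.

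**Working it through.** **The plan's own figures.** Section 10.2 gives 0.075 as the maximum interval width with 700 samples. The exact interval at 350/700 is 0.4623 to 0.5377, width 0.0754, so the figure reproduces. Section 5.5 plans 266 RET FISH tests, which also reproduces from Table 10 as 70 + 196. At 266 the maximum exact width is 0.123, so the 0.075 does not describe RET.

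**Inputs from Table 10 (Section 5.5), summed over four years.**

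- RET internal: 10+20+20+20 = 70 tested; 2+4+4+4 = 14 positive (20.0%).
- RET external: 28+56+56+56 = 196 tested; 1+1+2+2 = 6 positive (3.1%, exact 95% CI 1.1 to 6.5%).
- RET pooled: 20/266 = 7.5% (4.7 to 11.4%).
- FGFR1, of 700 tested: SISH+ISH+ 18+17 = 35; SISH+ISH- 28+28 = 56; SISH-ISH+ 49+49 = 98. Any SISH+ is 35+56 = 91 (13.0%).

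**Assumption.** k is the number of screened patients who came already known to be positive and are counted as positive. The documents give no value; 3, 5 and 10 are illustrative.

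**Formula.** Observed prevalence = (x + k)/(n + k).

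| k | RET pooled | RET external (all k external) |
|---|---|---|
| 0 | 20/266 = 7.5% | 6/196 = 3.1% |
| 3 | 23/269 = 8.6% | 9/199 = 4.5% |
| 5 | 25/271 = 9.2% | 11/201 = 5.5% |
| 10 | 30/276 = 10.9% | 16/206 = 7.8% |

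The pooled values all stay inside the k = 0 interval of 4.7 to 11.4%. The external value at k = 10 lies above its k = 0 upper limit of 6.5%.

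**FGFR1.** Ten known positives added to one group move SISH+ISH+ from 5.0% to 45/710 = 6.3%, SISH+ISH- from 8.0% to 66/710 = 9.3%, or SISH-ISH+ from 14.0% to 108/710 = 15.2%. Twenty known SISH positives would move any SISH+ from 13.0% to 111/720 = 15.4%.

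**The opposite direction.** Every patient is tested for FGFR1 first, and Section 5.5 treats RET and FGFR1 as mutually exclusive. Ten known RET positives would therefore join the FGFR1 denominator as presumed negatives: any SISH+ falls from 91/700 = 13.0% to 91/710 = 12.8%.

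**One group the documents do count.** Section 3.3 reports four RET positives among 20 internal pan-negative patients already tested. Whether they enter Part A is not stated. If only the four positives did, internal RET would go from 14/70 = 20.0% to 18/74 = 24.3%. If all 20 did, it would be 18/90 = 20.0%. The bias comes from selective entry, not from prior testing as such.

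**Enrichment by design.** Section 5.2.2 limits RET FISH to FGFR1 double negatives of eligible histology, only where standard care covers it, and for internal cases only to pan-negatives. Section 5.5 assumes 2% RET in adenocarcinoma but 20% in pan-negatives. Pooled RET is thus planned at 7.5% with no self-referral at all.

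**The case against.** The strongest reply is that the objective is met as written. It asks for prevalence in the screened populations, and people who answer the outreach belong to them. Against that literal target there is no bias. This stands. The difficulty arises when the figure is used to predict the yield of further screening in untested patients, or set beside microarray rates, and Section 10.2 plans both uses.

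A reader might infer that the estimate is inflated, and RET severely so. The documents do not support that. They give no count of known positives and do not say expressly that such patients are counted; inclusion is read from the absence of a rule. The near-doubling of external RET at k = 5 (3.1% to 5.5%) concerns a subset that Section 10.2 does not define as an estimate. The pooled figure moves from 7.5% to 9.2%.

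There are also reasons to expect few known results. Section 2.5 describes sequencing as too costly and scarce for wide screening, RET FISH is an in-house assay, and Section 5.1 aims remote consent at patients unlikely to be positive. Against this, Section 3.1 notes other trials that already select on FGFR1 amplification, so some patients will have a known result.

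For RET, the testing restrictions are a better documented source of enrichment than self-referral. This also stands, and separating known positives would not remove it.

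Finally, prior results are already collected, remote and local patients are contrasted descriptively, and Section 5.5 admits that preselection of external cases cannot be determined beyond captured results. These help, but none puts a rule into the estimate.

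**Conclusion.** The point holds as a gap in the analysis set, not as a demonstrated bias. Part A prevalence can be inflated as an estimate of yield in untested patients, because known positives are admitted, have a reason to come, and are not separated. RET is the most exposed marker: it is rare, has the smaller denominator, and is the named example for outside results. With 3 to 10 assumed known positives, pooled RET rises from 7.5% to between 8.6% and 10.9%, and external RET from 3.1% to between 4.5% and 7.8%. These figures assume that Table 10 is otherwise realised, that all k are counted as positive, and that known negatives do not come in proportion. Ten known positives move an FGFR1 group by 1.2 to 1.3 percentage points, and known RET positives could slightly lower FGFR1 prevalence.

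Even without self-referral, RET here should not be read as a general prevalence, because of whom the plan chooses to test. The estimate is descriptive and carries no hypothesis test, so this is a worthwhile, inexpensive improvement and not a threat to the trial's validity.

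**What to change.** 1. At Part A consent, record for each study marker whether a result was already known, what it was and by which assay.
2. In Section 10.2, base the main prevalence for each marker on patients whose status for that marker was unknown at consent. Report all screened patients as a sensitivity analysis, and list the previously tested patients separately.
3. Report RET by internal and external source, each with its own tested denominator, and state the testing restrictions beside the result.
4. Apply the same split at the 250 and 500 sample analyses and to the 85% enrollment measure.

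The cost is one registration field, since prior molecular results are already acquired, a few sentences in Section 10.2, and a slightly smaller denominator for the main estimate. The field should be in place before the first interim analysis.
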